9 SAFETY ANALYSIS

All patients randomised will be included in the safety analysis.

All serious adverse events (SAE) occurring during the trial enrolment period shall be detailed and reported by randomised group. The overall incidence of patients experiencing at least one SAE will be compared between the randomised groups using a chi-squared test and the difference in proportions with 95% confidence intervals will be presented. Where a patient reports more than one of the same type of event, separate tables will be presented showing a) counts of events and b) counts of patients experiencing at least one type of this event.

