9.1 ADVERSE EVENTS

The potential risks to patients of the research may include a fall (either in the HAH setting or inpatient setting), hospital acquired infection for patients randomised to inpatient admission, hospital admission for those randomised to HAH, post-discharge hospitalisation and death for all patients. All SAEs occurring during the study, either observed by the recruiting clinician or reported by the patient, will be recorded on the AE Log CRF and SAE Log CRF. All SAEs will be recorded whether or not attributed to the HAH with CGA intervention. All SAEs will be forwarded by the site to the PC-CTU and the trial manager, using the "PC-CTU SAE Report Form" following assessment for seriousness by the site clinician. Adverse events will be summarised descriptively according to randomised group, no statistical comparison will be undertaken on this data.

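### Serious falls and hospital-acquired infection, both named as risks, have no planned between-arm estimate, and the pooled any-SAE comparison is insensitive to a change in either

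*SAP*

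**What the plan says.** Section 9 of the SAP sets the safety population ("All patients randomised will be included in the safety analysis") and plans a by-arm account of SAEs: "All serious adverse events (SAE) occurring during the trial enrolment period shall be detailed and reported by randomised group". The one comparison is on the pooled endpoint: "The overall incidence of patients experiencing at least one SAE will be compared between the randomised groups using a chi-squared test". For its effect measure, the same sentence adds that "the difference in proportions with 95% confidence intervals will be presented".

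Type-level results come in a sentence that opens with a condition, "Where a patient reports more than one of the same type of event", and continues: "separate tables will be presented showing a) counts of events and b) counts of patients experiencing at least one type of this event".

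Section 9.1 lists the risks the trial expects. It begins "The potential risks to patients of the research may include a fall (either in the HAH setting or inpatient setting" and goes on to hospital-acquired infection in the inpatient arm, hospital admission in the hospital-at-home (HAH) arm, and post-discharge hospitalisation and death in both. After describing how SAEs are recorded and forwarded, it ends by saying that adverse events are summarised descriptively by arm and that "no statistical comparison will be undertaken on this data".

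Section 5.1 gives two of these risks their own models as secondary outcomes: mortality (item 3), and readmission or transfer to hospital (item 7). Falls and hospital-acquired infection appear in no model.

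**The concern.** The named risks do not all point the same way. Section 9.1 ties infection to the inpatient arm and admission to the HAH arm. An endpoint that counts a patient once for any SAE adds these together, so an excess of one type can be offset by a deficit of another. In a frail, acutely ill population, many patients may also have some SAE whatever their arm. A patient who falls and is counted already for another event adds nothing to the endpoint.

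Falls are foreseeable here: the inclusion criteria in section 2.2 cover patients who present with them. At stake is whether the report will contain a pre-planned estimate, with its uncertainty, of the difference in a harm that the SAP itself anticipates. Without one, a reader has only an any-SAE result that says little about that harm in either direction.

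**Working it through.** **Inputs from the SAP.** Section 2.3 gives 1050 patients at 2:1 and a significance level of 0.05 (taken as two-sided). Section 9 includes everyone randomised, so the arms are 1050/3 = 350 inpatient and 700 HAH.

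**The SAP's own figure.** It states no power for safety. Its primary-outcome figure does reproduce: 50% v 40%, 2:1, 83% power with continuity correction needs 329 controls, or 987 in total, and 987/0.94 = 1050.

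**Assumptions, because the SAP gives no SAE rates.** Serious falls are 3% or 5% in the inpatient arm and double under HAH. Other SAEs affect a proportion *o* of patients, from 30% to 70%, equal in both arms and independent of falls.

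**Formulas.** In each arm, P(any SAE) = 1 − (1 − *o*)(1 − *fall*). With difference *d*, pooled null standard error s0 and unpooled standard error s1, two-sided power = Φ((d − 1.96·s0)/s1) + Φ((−d − 1.96·s0)/s1).

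**Example, falls 5% v 10%, *o* = 60%.** Inpatient: 1 − 0.40 × 0.95 = 62.0%. HAH: 1 − 0.40 × 0.90 = 64.0%. So d = 0.020, s0 = 0.0315, s1 = 0.0317, and power is about 10%.

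| Other SAEs | Any SAE, falls 3% v 6% | Power | Any SAE, falls 5% v 10% | Power |
|---|---|---|---|---|
| 30% | 32.1% v 34.2% | 10% | 33.5% v 37.0% | 20% |
| 50% | 51.5% v 53.0% | 7% | 52.5% v 55.0% | 12% |
| 60% | 61.2% v 62.4% | 7% | 62.0% v 64.0% | 10% |
| 70% | 70.9% v 71.8% | 6% | 71.5% v 73.0% | 8% |

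**Falls compared on their own, same formula.**
- 3% v 6%: s0 = 0.0143, s1 = 0.0128, power 56%. Expected difference 3.0 points, 95% CI about 0.5 to 5.5.
- 5% v 10%: s0 = 0.0181, s1 = 0.0163, power 81%. Expected difference 5.0 points, 95% CI about 1.8 to 8.2.

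**Larger excess.** With falls at 10% v 20%, the any-SAE test has 58% power at *o* = 30% and 19% at *o* = 70%, against 99% for falls alone. Dilution is weaker, but still marked.

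**Offsetting.** Take falls at 5% v 10% and let other SAEs be 60% inpatient and 58% HAH. Any SAE is then 62.0% v 1 − 0.42 × 0.90 = 62.2%. A doubling of serious falls leaves a difference of 0.2 points.

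**The case against.** A reader might infer that harm is compared only through the any-SAE proportion. It is not. Mortality at 6 and 12 months, and readmission or transfer at 1 and 6 months, have their own models with adjusted relative risks, confidence intervals and p-values. New residential care and delirium are modelled too.

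A reader might also infer that an excess of falls would be hidden. The SAP does not support that either, since SAEs are to be detailed by arm. On the 3% v 6% assumption, about 42 of 700 and 10 or 11 of 350 patients would have a serious fall, and anyone with those counts and the denominators could form the difference. What is missing is the planned estimate and interval. Two points limit this defence. The patient-level tables by type are conditional on repeat events, so a harm that happens once per patient might not get one. And under 2:1 allocation raw counts mislead, because equal risks give twice as many events in the HAH arm.

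A third tempting inference is that section 9.1 forbids any comparison of SAE types. Read that broadly, it would also forbid the any-SAE test that section 9 prescribes. The more natural reading is that it covers adverse events outside that comparison. But the sentence follows text about recording SAEs, so its scope should be stated.

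Testing one overall proportion and describing the rest is a defensible way to avoid many sparse comparisons, and the SAP nowhere says that a null any-SAE result will be read as equal safety. That argues against adding significance tests. It does not argue against two descriptive intervals. The fall and SAE rates above are assumptions, which is why a range is shown.

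**Conclusion.** The point holds in a limited form. The only planned between-arm SAE estimate is a pooled proportion, and it responds weakly to a change in one event type: roughly 6% to 20% power for a doubling of serious falls from 3% or 5%, against about 56% and 81% for falls alone. These figures rest on 350 and 700 patients, on other SAEs in 30% to 70% of both arms, and on independence between falls and other SAEs. The size varies with these rates, but the direction was the same in every case tried. The gap covers falls and hospital-acquired infection, not death or readmission. It concerns estimation and table wording, and it is cheap to close.

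**What to change.** In section 9:
- For SAEs that are falls, and for SAEs that are hospital-acquired infections, report by arm the number and percentage of patients with at least one such event, with the difference in proportions and 95% CI. Label these descriptive and give no p-values.
- Produce the by-type tables of events and of patients for every SAE type, without the condition that a patient has repeat events.

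In section 9.1, state that the sentence ruling out statistical comparison applies to non-serious adverse events.

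Death and readmission or transfer need no extra interval here, because section 5.1 covers them. The change is to SAP wording only and uses SAE data that are already recorded and reported by arm. The cost is two further unadjusted intervals, which may be wide if events are few.

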6) Known cognitive decline at baseline (IQCODE)

The Short Form of the Informant Questionnaire on Cognitive Decline in the Elderly (IQCODE) [4] is assessed at the patients baseline visit only. IQCODE is a 16 item questionnaire (variables *iqcode1 – iqcode16*), each question has a possible range of scores from 1 to 5. To obtain the mean IQCODE score for each participant take the mean of all IQCODE items available for that participant. Participants will still have their mean IQCODE score calculated if they are missing several items, participants will only be missing their mean IQCODE score if they are missing every item. Randomisation was stratified by IQCODE score ≥ 3.5

7) Quality of life at baseline and 6 months

Quality of life is measured by EQ-5D-5L scores [5], and is assessed at baseline and 6 months follow-up. EQ-5D-5L index scores will be computed as per the EQ-5D-5L user guide (version 2.1 April 2015).

8) Quality adjusted survival at 6 months and 12 months

Quality adjusted survival will be analysed as part of the economic evaluation and the methods will be detailed in a separate analysis plan.

9) Length of hospital stay over 6 months from randomisation

Number of nights spent in hospital between baseline and 6 months follow-up is collected on the health service use CRF.

10) Readmission or transfer to hospital at 1 month and 6 months

Subsequent admissions to hospital is measured at 1 month, and 6 months follow-up (variable *hadmityn*). Subsequent admissions to hospital is a binary variable (0 = No, 1 = Yes). The 6 months admission to hospital data will include the data collected at the 1 month time point. Number of days spent in hospital at 1 month, and 6 months after baseline will not be considered in the main statistical analysis, this data will be analysed as part of the economic evaluation and the methods will be detailed in a separate analysis plan.

11) Resource use (health and social care and informal care) at baseline and 6 months

Resource use will be analysed as part of the economic evaluation and the methods will be detailed in a separate analysis plan.

12) Costs and cost-effectiveness

Costs and cost-effectiveness will be analysed as part of the economic evaluation and the methods will be detailed in a separate analysis plan.

13) 'Living at home' at 12 months

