2.3 SAMPLE SIZE

The sample size is calculated for the primary outcome: living at home at 6 months follow up (the inverse of death or living in a residential care setting), for a 2:1 randomisation ratio with 2/3rd randomized to admission avoidance HAH with CGA and 1/3 to inpatient CGA. Several sources informed our estimate of effect size; these were one of the trials included in the IPD meta-analysis of HAH which recruited frail older people who required hospital level care (similar to the study population we plan to recruit), an audit of 750 patients who received HAH + CGA in Lanarkshire, the RCTs of CGA included in the Cochrane Review and the pooled estimate for the relative effect at 6 months obtained from the IPD Cochrane Review of HAH (3 trials, 607 participants) which was an adjusted Hazard Risk of 0.62 (95% CI 0.45 to 0.87) for mortality. Our proposed study effect estimate is based on a control group (CGA hospital) event rate at 12 months of 50% with a 10% reduction in living in a residential setting to 40% in the CGA at home group, equal to a relative risk of 0.8 which lies towards the top end of the 95% CI for the pooled estimate. We have calculated that a sample size of 1050 to achieve around 83% power at a significance level of 0.05 to detect a 10% absolute difference, assuming a control group event rate at 12 months of 50% and 6% attrition.

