2.4 RANDOMISATION AND BLINDING IN THE ANALYSIS STAGE

Following informed consent and the collection of baseline data eligible patients will be randomly allocated using a 2:1 ratio (2 admission avoidance HAH with CGA: 1 inpatient CGA) by the local member of the research team who recruited the participant. Randomisation will be performed using Sortition, Oxford University's Primary Care Clinical Trail Unit's in-house online randomisation system. Randomisation will be stratified by centre (Bradford, Newport Lanarkshire, Lothian, Fife, Royal Devon Exeter, Torfaen, North Deon, Southern Trust, Guys & St. Thomas, and Belfast), gender and by known cognitive decline.

We have opted for a 2:1 ratio as the HAH schemes have been established to ease the pressure on acute hospital beds and concern was expressed by the clinical leads that a 1:1 randomisation ratio would place unmanageable pressure on the inpatient service. This was therefore a decision related to the capacity of the service to manage patients in the two settings. This has been taken into account in our analysis plan and will not affect the estimated precision of our findings.

Due to the nature of the intervention, it is not possible to blind participants. It will also not be possible to blind research nurses who will collect outcome data as participants will know which intervention they will have received (admission avoidance HAH with CGA or inpatient admission) and are likely to discuss this with the nurse.

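### The SAE comparison in section 9 ignores the factors that stratified randomisation: valid, but mildly conservative if those factors predict SAEs, and out of line with the SAP's other between-arm analyses

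*SAP*

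**What the plan says.** - **Section 9 (Safety analysis).** "All patients randomised will be included in the safety analysis". The proportion with one or more SAEs is to be "compared between the randomised groups using a chi-squared test and the difference in proportions with 95% confidence intervals will be presented". No stratification factor or covariate is mentioned. Under section 9.1, adverse events are only described, so this is the one formal test in section 9.
- **Section 2.4 (Randomisation).** "Randomisation will be stratified by centre", and also by "gender and by known cognitive decline". Section 2.1.2, item 6, gives the cut used for the last factor: "Randomisation was stratified by IQCODE score ≥ 3.5".
- **Sections 4.1 and 5.1.** The primary model and all seven secondary analyses include gender and IQCODE as fixed effects and centre as a random effect. Section 4.1 also allows centres with few patients to be grouped.
- **Section 3.4.** Centre differences are said to be dealt with by the primary and secondary analyses. The safety analysis is not mentioned.
- **End of section 5.1.** A chi-squared test is a fallback for failed model assumptions, and the SAP notes that it rules out covariate adjustment. In section 9 the same test is the planned method, and no reason is given.

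**The concern.** When allocation is balanced within strata, differences in event rate between strata cancel out of the treatment contrast. A crude standard error does not know this and still counts those differences as noise. If the strata are prognostic, the crude interval is wider than it need be and the test rejects below its nominal level. For a harm comparison, that slightly lowers the chance of seeing a true excess of SAEs in one arm.

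Centre could plausibly matter. SAEs are reported "following assessment for seriousness by the site clinician", so the judgement is made locally, and several of the risks listed in section 9.1 are hospital admissions, which depend on local services.

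There is also a question of consistency. Death and hospital admission are listed as risks in section 9.1 and are analysed with adjustment in section 5.1. One report would then show overlapping events by adjusted and unadjusted methods, on different scales.

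**Working it through.** **1. The SAP's own figure.** The SAP states no SAE rate, SAE power or interval width. Its only design figure is for the primary outcome: "1050 to achieve around 83% power at a significance level of 0.05 to detect a 10% absolute difference", "for a 2:1 randomisation ratio with 2/3rd randomized to admission avoidance HAH with CGA and 1/3 to inpatient CGA", with 50% versus 40% and 6% attrition.

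- Uncorrected control-arm size: n = [z(0.975)·√(1.5·p̄·q̄) + z(0.83)·√(0.5·0.5 + 0.4·0.6/2)]² / 0.10², with p̄ = (0.5 + 2·0.4)/3 = 0.433. This gives 313.3.
- With continuity correction: (313.3/4)·[1 + √(1 + 6/(313.3·2·0.10))]² = 328.1, so 329.
- 3 × 329 = 987 evaluable, and 987/0.94 = 1050.

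The figure is reproduced. It has no bearing on the SAE comparison except to supply N = 1050, that is 700 and 350 patients.

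**2. Closed form, centre only.** Assumptions: overall SAE proportion p = 40%, exact 2:1 allocation within 11 equal centres, and evenly spaced centre rates with standard deviation s.

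- Crude SE = √[p(1−p)(1/700 + 1/350)] = √(0.24 × 0.004286) = 0.0321.
- Within-centre variance = p(1−p) − s².
- Crude SE / stratified SE = √[0.24/(0.24 − s²)].
- Implied centre rates run from 0.40 − (5/√10)s to 0.40 + (5/√10)s.
- Null rejection rate of the crude test = P(|Z| > 1.96 × ratio).

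| s | Implied centre rates | Excess crude SE, formula | Excess crude SE, simulated | Null rejection of crude test, formula | Null rejection of crude test, simulated | Power at a 9-point difference, crude → stratified (simulated) |
|---|---|---|---|---|---|---|
| 5 points | 32–48% | 0.5% | about 0% | 4.9% | 5.1% | 79.7 → 79.9% |
| 10 points | 24–56% | 2.2% | 2% | 4.5% | 4.9% | 79.7 → 80.8% |
| 15 points | 16–64% | 5.0% | 5% | 4.0% | 4.3% | 80.9 → 83.5% |
| 20 points | 8–72% | 9.5% | 9% | 3.2% | 3.3% | 81.6 → 86.3% |

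Each simulated entry rests on 10,000 trials (Monte Carlo SE about 0.22 points at 5%). The stratified test itself rejected at 5.5% and 5.4% under the null for s = 10 and 15 points, so part of the small power gain in those rows may come from a slightly liberal test.

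**3. All three factors.** Assumptions: 10 centres of unequal size × gender × IQCODE, near-exact 2:1 allocation within strata, no treatment effect, and 3,000 trials per scenario. The crude Wald interval is compared with the Mantel-Haenszel interval (Sato variance). Full 95% CI widths are in percentage points, crude / stratified, with the excess taken from unrounded widths.

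| Strata effects (centre SD on logit scale; OR gender; OR IQCODE) | SAE rate 15% | SAE rate 30% | SAE rate 50% |
|---|---|---|---|
| None (0; 1; 1) | 9.13 / 9.17 (−0.4%) | 11.75 / 11.79 (−0.4%) | 12.82 / 12.86 (−0.3%) |
| Mild (0.3; 1.2; 1.3) | 9.25 / 9.22 (+0.3%) | 11.78 / 11.70 (+0.7%) | 12.80 / 12.68 (+0.9%) |
| Moderate (0.5; 1.3; 1.6) | 9.47 / 9.31 (+1.7%) | 11.84 / 11.54 (+2.6%) | 12.77 / 12.40 (+3.0%) |
| Strong (0.8; 1.5; 2.0) | 9.78 / 9.34 (+4.8%) | 11.91 / 11.19 (+6.5%) | 12.72 / 11.88 (+7.1%) |

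The full width changes by 0.03 to 0.37 points in the mild and moderate rows and by 0.44 to 0.84 points in the strong row. Coverage of the crude interval lies between 94.4% and 96.7% (simulation error about 0.4 points).

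**4. Cell sizes.** Ten centres × 2 × 2 gives 40 strata. 1050/40 is about 26 patients per stratum, of whom about 9 are controls. With unequal centres some strata will be nearly empty, so full three-factor stratification may not be workable everywhere.

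**The case against.** The strongest reply is that a crude comparison of an SAE proportion is conventional, prespecified and valid under randomisation. Ignoring the strata errs, if at all, on the conservative side. Section 9 contradicts nothing, and the SAP gives no data showing that SAE rates differ by stratum. All of this stands, and it limits the size of the point. It does not remove the conservative standard error where strata are prognostic, nor the mismatch with every adjusted model in the same plan.

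A reader might infer more than the document supports:

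- **That this is the only harm tested.** It is not. Mortality is tested with an adjusted relative risk (section 5.1, item 3). Readmission or transfer is modelled with the same adjustment (item 7, where the reporting sentence names activities of daily living).
- **That the interval is too wide as a matter of fact.** This depends on the strata predicting SAEs. With no strata effects the crude interval is marginally the narrower one.
- **That sites were selected because provision varies.** Section 1.4 states an aim to investigate generalisability across such settings. It does not say how sites were chosen. Local judgement of seriousness makes centre differences plausible but does not show them.
- **That about 5 points of power are being lost.** That needs control SAE rates from roughly 8% to 72% across centres, and nothing in the SAP suggests such a spread.

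It is also fair to object that a Mantel-Haenszel risk difference would still not share a scale with the adjusted relative risks for mortality and readmission. Only the model-based option resolves that.

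**Conclusion.** The point holds as a minor matter of efficiency and consistency. The planned SAE comparison is valid but leaves out factors that governed allocation and that the SAP adjusts for elsewhere. Its 95% interval would be about 0–3% too wide under no-to-moderate strata effects and up to about 7% under strong ones. At a 30% SAE rate with moderate effects, that is a full width of 11.8 rather than 11.5 points.

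These sizes rest on assumed SAE rates (15–50%), assumed strata effects, N = 1050, and near-exact 2:1 balance within strata, for which the SAP states no blocking scheme. More extreme centre differences, as in the last row of the centre-only table, would give a larger excess but are not supported by anything in the SAP. If the strata carry no information, stratifying costs about 0.3–0.4% of interval width. The change is therefore close to free, but it is unlikely to alter a conclusion.

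**What to change.** In section 9, replace the chi-squared test as the between-arm comparison with one of the following:

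1. A Mantel-Haenszel risk difference with 95% CI and a Cochran-Mantel-Haenszel test, stratified by centre (small centres grouped as in section 4.1) and, where cell sizes allow, by gender and IQCODE ≥ 3.5.
2. The section 4.1 model fitted to the outcome of at least one SAE. This also puts the result on the same scale as mortality and readmission.

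State in advance which option is used and, for option 1, the rule for falling back to centre only when cells are sparse. Keep the crude counts, percentages and difference per arm as description. When defining centre, settle whether Newport and Torfaen form one stratum or two: section 2 joins them and section 2.4 lists them apart. The effect on the numbers here is immaterial.

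Cost: a short amendment to the SAP and a few lines of code. No new data are needed, since the stratification factors are known at randomisation.
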